We enhanced the motivation phase of the conceptual model with additional components drawn from risk perception and communication research. Comprehension of information was added because perceptions and comprehension are slightly different constructs that each have an important role in influencing health behavior and decisions.^[11] Worry, affective reaction to the information, affective attitudes to exercise, and anticipated regret were added because a growing body of research demonstrates that affect and emotion are integral to the formation of risk perceptions, in increasing motivation to change behavior, and in changing behavior itself.^[12-17] Demographics, numeracy, health literacy, and graph literacy were added because they are associated with the ability to understand and use health risk information.^[18-20]

According to HAPA, progression to the **action phase** is dependent upon factors not included in the motivation phase. These new factors include developing action plans for engaging in the behavior, coping plans for overcoming barriers to action, maintenance self-efficacy (i.e., confidence in the ability to overcome barriers to acting), and recovery self-efficacy (i.e., confidence in the ability to recover from a relapse).

Objectives

RISK CALCULATOR

To compare the effectiveness of communicating personalized risk estimates via text, table, or risk ladder.

Primary outcomes hypotheses and exploratory research questions

H1: Comprehension of risk information and intentions to increase physical activity will be higher among individuals who see multiple disease risks presented as a risk ladder than as text.

RQ1: Prior research has shown that tables can be effective in communicating risk information.^[21] Compared to the table, will the risk ladder elicit higher comprehension and intentions?

Secondary outcomes hypotheses and exploratory research questions

H2: Any significant effect of the risk ladder on intentions will be mediated by comprehension, risk perceptions, response efficacy, worry, affective reactions to information, affective attitudes to exercise, and anticipated regret.

H3: Engagement in physical activity will increase from baseline to 90 day follow-up to a greater extent for individuals who see the risk ladder than those who see text only.

H4: Intentions will mediate any significant effect of the risk ladder on physical activity.

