The research staff will be blinded to participants' risk presentation conditions, but they will be unblinded to the mental imagery condition. This unblinding was the result of a combination of the block randomization (which prevented us from preparing packets of study materials ahead of time and assigning participants to condition in order of completion (e.g., A, B, C, D, E, F)), and the need for the goal cards and Baseline Survey 2 to include information specific to the mental imagery condition the participant was assigned to (see below).

Procedure

The procedures for the study will occur in 3 parts. Part 1 is an initial 45 minute data collection session in person, followed by (Part 2) reminders and surveys conducted by Short Message Service (SMS) text messaging over the subsequent 4 weeks, and (Part 3) a final mailed survey on paper. The last half of Part 1 and all of Part 2 are adapted from prior research conducted by [name] for use with University of Auckland employees.^[5, 9] We worked closely with [name] to adapt the interventions so they would be acceptable to our St. Louis community sample (e.g., minimize burden, reduce the need for Internet access, to accommodate cell phone plans that do not have unlimited text and/or data, etc). This adaptation was performed in Spring 2017 and involved 3 sets of cognitive interviews, each set including 6-7 participants (Aim 2, Part 1).

Part 1, Baseline Intervention Administration and Data Collection. Participants will complete all baseline activities in person with a research assistant. After completing eligibility screening and informed consent processes, participants will use a smartphone provided by research staff to complete the risk calculator portion of the study. The research assistant will enter the participant ID into the responsive website, and then the participant will provide information about their demographics, health behaviors, and personal and family health history (Appendix A Aim 2, Risk Display App Screens, pg. 2-34). The website then provides participants with personalized risk results for their current activity level and how it would change if they began exercising regularly. Results are displayed either as alphanumeric text, table, or risk ladder (Appendix A Aim 2, Risk Display App Screens, pg. 35-38). Afterwards, the participant will complete Baseline Survey 1 independently on paper (Appendix C, Instructions Appendix HH).

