To reduce participant burden, we limit the number of survey questions by adapting single item measures used in nationally representative surveys and in published empirical research. Many items are identical or very similar to the items in Aim 1 and Aim 2, Part 1 of the study. All items for the proposed research, including items that were adapted or developed specifically for Aim 2, Part 2, underwent cognitive testing in either Aim 2, Part 1 or in prior research studies conducted by the [name] Lab. Adaptations to the items intended for use in the text messaging surveys (160-character limit) were made in close collaboration with [name], who was the initial developer of the interventions. Table 1 below provides each of the measures that will be assessed in each part of the survey.

Table 1. Summary of Study Measures, in Order of Completion

Questionnaire Name	Timing	Content
Part 1: Baseline		
Eligibility Screener (Appendix H)	Pre-randomization	Age; ^[23] race/ethnicity; ^[23] education; ^[23] personal diagnosis of the target diseases; ^[24, 25] physical activity behavior; ^[26, 27] and cell phone access (developed in-house)
Risk Assessment (Appendix A)	Immediately following randomization to 1 of 6 conditions in a 3 (risk presentation: text vs. table vs. risk ladder) x 2 (mental imagery: physical activity vs. sleep hygiene) design	Demographic, biological, and behavioral characteristics needed for the risk algorithm ^[28-30]
Baseline Survey 1 (Appendix C)	Immediately following provision of personalized risk information	Comprehension; ^[31] cognitive and affective perceived risk; ^[32] perceived severity ^[33] worry; ^[32] response efficacy; ^[34] action self-efficacy; ^[35] affective reaction to the information; ^[36] affective attitude about exercise; ^[16] anticipated regret; ^[17] intentions to engage in physical activity in the next 90 days; ^[34] numeracy ^[37] ; graph literacy; ^[20] health literacy. ^[38] self-reported health status; ^[24] work schedule; ^[39] sleep behavior. ^[9] Other items intended to be used as preliminary data in future studies examining possible defensive processing of personalized health risk information include: perceived accuracy of information; ^[4, 40] message acceptance; ^[41] defensive processing ^[42] time orientation, ^[43] and spontaneous self-affirmation. ^[32]

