Baseline Survey 2 (Appendices L and M)	Immediately following completion of the mental imagery activity. The specific item wording is tailored based on which mental imagery condition is assigned (i.e., mental imagery vs. sleep), but the constructs assessed are the same for both conditions.	Message acceptance, ^[41] perceived clarity and vividness of images; ^[5, 9] and the following items obtained, developed, or adapted from: ^[5, 6, 9, 34] action plan; coping plan; action self-efficacy; recovery self-efficacy; and maintenance self-efficacy.
--	--	--

Part 2: Text Messaging

Mid-Intervention Text Message Surveys (Appendices X and Y)	1, 2, 3, and 4 weeks after Part 1	Perceived clarity and vividness of images; ^[5, 9] and the following items obtained, developed, or adapted from: ^[5, 6, 9, 34] action plan; coping plan; action self-efficacy; recovery self-efficacy; and maintenance self-efficacy.
--	-----------------------------------	--

Part 3: 90-Day Follow-Up

Follow-Up (Appendix BB)	90 days after Part 1	Comprehension; ^[31] physical activity behavior, ^[26, 27] sleep behavior, ^[9] tobacco use, ^[27] and the same items as in Baseline Survey 2 assessing intentions, action self-efficacy, cognitive and affective perceived risk, response efficacy, anticipated regret, and affective attitudes.
-------------------------	----------------------	---

Note: Race and education will be assessed during eligibility for recruitment stratification purposes only. Baseline Survey 1 excludes characteristics that will be assessed in the Risk Assessment questionnaire.

Statistical Considerations

Preliminary Analyses

We will begin by using descriptive statistics to understand the frequency and distributional properties of all items. For variables with non-normal distributions, data transformations or non-parametric tests will be used for subsequent analyses.

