All hypotheses and research questions will be examined using separate analyses for each outcome variable. Assumptions of each type of test will be checked (e.g., assumptions of normality and homogeneity of variance for ANOVAs). If there are violations, non-parametric tests will be used instead. Sex will be a covariate because there are no valid prediction models for male breast cancer, so men will not be shown a breast cancer risk estimate. The inclusion of other personal characteristics as covariates will be determined by the results of the preliminary analyses. Tests of moderation will be conducted by creating interaction terms between the risk presentation condition or mental imagery condition variables, as appropriate, and the variable assessing the moderator of interest. All statistical tests will be based on list-wise deletion except structural equation models, which can accommodate missing data.

Mediation analyses will be conducted using structural equation modeling (SEM). Full Information Maximum Likelihood estimation (FIML)^[44] will be used to allow the inclusion of missing data. Standardized estimates will be calculated and bias-corrected bootstrapping will be used to obtain the 95% confidence intervals.^[45-48] Criteria assessing model fit will also be examined (e.g., Standardized Root Mean Square Residual $\leq .08$, comparative fit index $\geq .95$, root mean square error of approximation $\leq .06$).^[49, 50] Mediation analyses will examine each construct as an individual mediator first, and then as a multiple mediator model.

Table 2 below describes the analyses that will be conducted for each hypothesis or research question.

Table 2. Overview of Statistical Analyses

	Priority	Statistical test(s)	Outcomes	Predictors/Mediators/Moderators
Risk Calculator				
H1; RQ1	Primary	3 arm ANOVA, 2 planned contrasts (risk ladder vs. text; risk ladder vs. table)	Comprehension, intentions	Predictor: Risk presentation condition
H2	Secondary	SEM	Intentions	Predictor: Risk presentation condition (risk ladder vs. text) Mediators: comprehension, risk perceptions, response efficacy, worry, affective reactions to information, affective attitudes to exercise, anticipated regret
H3	Secondary	3 arm ANOVA, planned contrast (risk ladder vs. text)	Change in physical activity (mins/week at 90 days – mins/week at baseline)	Predictor: Risk presentation condition

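### H2 claims mediation from constructs and intentions measured once, in the same post-display survey; a construct the ladder moves by about d = 0.3 can pass as a mediator with no causal effect

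*Combined protocol and SAP*

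**What the plan says.** H2 (Objectives, Risk Calculator, secondary) reads: "Any significant effect of the risk ladder on intentions will be mediated by comprehension, risk perceptions, response efficacy, worry, affective reactions to information", followed by affective attitudes to exercise and anticipated regret. Table 2 tests it by SEM for ladder versus text with intentions as the outcome.

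Table 1 places Baseline Survey 1 "Immediately following provision of personalized risk information", and the Procedure section says: "Afterwards, the participant will complete Baseline Survey 1 independently on paper". That one survey holds "Comprehension; ^[31] cognitive and affective perceived risk; ^[32] perceived severity ^[33] worry; ^[32] response efficacy", affective reaction, and "affective attitude about exercise; ^[16] anticipated regret; ^[17] intentions to engage in physical activity in the next 90 days". So all seven mediators and the outcome are there.

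Before the display the plan collects the eligibility screener (including physical activity) and the Risk Assessment, described as "Demographic, biological, and behavioral characteristics needed for the risk algorithm". No mediator and no intention item is listed in either.

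Under Main Analyses, indirect effects get bias-corrected bootstrap 95% intervals, and "Mediation analyses will examine each construct as an individual mediator first, and then as a multiple mediator model". Sex is always a covariate. Other personal characteristics enter if they differ between arms or are significantly associated with the outcomes. The plan states no assumption about mediator-outcome confounding and gives no sensitivity analysis for it.

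**The concern.** Only the display is randomised. The path from a construct to intentions is a correlation between answers given on one form at one sitting. It can reflect stable motivation, general affect, response style or the reverse order, as well as a causal effect.

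The plan's own theory makes some shared cause likely. The Background says that affect contributes both to risk perceptions and to motivation, so a single-mediator model for perceived risk leaves out a common cause that the authors expect. The plan also uses time ordering elsewhere: H6 and RQ6 take predictors from an assessment before the one that ends the change in activity. H2 has no such ordering.

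At stake is the explanatory claim. If the ladder raises intentions and also raises, say, response efficacy, the plan followed exactly can report response efficacy as the mechanism when it does nothing to intentions.

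**Working it through.** **1. The plan's own figure.** Inputs from Sample Size Calculations: three groups, f = 0.15, α = .05, 80% power. Noncentrality = N·f² = 432 × 0.0225 = 9.72. Power is 0.801 at N = 432 and 0.798 at N = 429, so 432 is the smallest multiple of three that suffices. 432/0.90 = 480. Both stated figures reproduce. The plan gives no figure for H2. Equal allocation gives 432/3 = 144 per risk arm, so 288 for ladder versus text.

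**2. A model with no mediation.** Let T be ladder (1) or text (0).
- Construct: M = d·T + z₁
- Intentions: Y = 0.3·T + r·z₁ + √(1 − r²)·z₂

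M has no effect on Y; they share only a residual correlation r. Regressing Y on T and M still gives a coefficient near r. The estimated indirect effect therefore centres on d·r, for example 0.3 × 0.3 = 0.09, when the truth is 0.

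Assumptions: d = 0.3 is the planning value for comprehension and intentions only, and is assumed for the other six constructs. The documents give no value of r; 0 to 0.5 is examined.

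**3. Hand check.** A false declaration needs both paths to be significant, so its probability is roughly P(a significant) × P(b significant).
- Path a, d = 0.3: 0.3 × √72 = 2.55, power 0.718. At d = 0.15: 1.27, power 0.245. At d = 0: 0.05.
- Path b, Fisher z with √(288 − 4) = 16.85. At r = 0.1: 0.1003 × 16.85 = 1.69, power 0.394. At r = 0.2: 0.2027 × 16.85 = 3.42, power 0.927. At r = 0.3: 0.3095 × 16.85 = 5.22, power 0.999.
- Products at d = 0.3: r = 0.1, 0.28; r = 0.2, 0.67; r = 0.3, 0.72.
- Products at d = 0.15: r = 0.2, 0.23; r = 0.3, 0.24.
- Product at d = 0, r = 0.3: 0.05.

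**4. Simulation, single-mediator model.** 144 per arm, bias-corrected bootstrap 95% interval, 500–600 trials with 500–600 resamples each. Percentage of trials in which the non-causal construct is declared a mediator:

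| Ladder effect on construct | r = 0 | r = 0.1 | r = 0.2 | r = 0.3 | r = 0.5 |
|---|---|---|---|---|---|
| d = 0.3 | 5 | 33 | 74 | 78 | 76 |
| d = 0.2 | 4 | 19 | 44 | 44 | 41 |
| d = 0.1 | 1 | 11 | 16 | 17 | 14 |
| d = 0 | 0 | 3 | 8 | 5 | 5 |

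Monte Carlo intervals for the product, in place of the bootstrap, give at d = 0.3 about 26% (r = 0.1) and 67–74% (r = 0.2–0.4), and at d = 0.15 about 22–26% (r = 0.2–0.4). Together the two methods give 67–78% at d = 0.3 with r of 0.2 or more, and 26–33% at r = 0.1.

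H2 applies only when the ladder effect on intentions is significant. Among those trials the bootstrap rate at d = 0.3 is 77–84% (r = 0.2–0.5).

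**5. Simulation, joint model.** Seven non-causal constructs, all moved by d = 0.3, all residual correlations equal to 0.3 or 0.5; 150 trials, 300 resamples. Each construct is declared in 43–50% of trials, against 76–77% in the single models. At least one is declared in 97–99%.

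**6. Can the data tell a true mediator from a false one?**
- In the single-mediator linear model, the residual correlation that sets the indirect effect to zero equals the observed treatment-adjusted correlation. It is about 0.30 for a false mediator with r = 0.3 and about 0.29 for a true one with coefficient 0.3.
- With 90-day intentions, the plan's 30% attrition leaves 500 × 0.70/3 ≈ 117 per arm. If r stays at 0.3, a false mediator with d = 0.3 passes in about 63–66% of trials; a true one with the same d and coefficient 0.3 passes in about 62%.

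Neither quantity separates the two cases.

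**The case against.** The strongest reply is that the high rates occupy one part of an assumed grid. The documents give no construct-intentions correlation, and f = 0.15 was set for comprehension and intentions, not for worry, regret or affect. With a weaker ladder effect or a correlation of 0.1 the rate falls well below one half. The joint model lowers it per construct. The plan already adjusts for sex and for characteristics found to matter. The causal ordering comes from a stated theory, and H2 is secondary and applies only after a significant ladder effect.

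Most of this stands, and it limits the size of the point. A reader might infer that any construct correlated with intentions will usually be declared a mediator. The documents do not support that: correlation alone gives about 5%, because the ladder must also move the construct. A reader might also infer that the plan makes no attempt to control confounding. It does, but only for measured characteristics that happen to reach significance.

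The reply does not remove the problem. The joint model still declares non-causal constructs in 43–50% of trials under the stated assumptions. A theory of ordering is also not evidence for it when everything is measured at one time.

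**Conclusion.** The point holds in conditional form. H2's wording is causal, while its construct-to-intentions path is an unprotected same-survey correlation with no stated assumption and no sensitivity analysis. For a construct that the ladder moves by about d = 0.3 and whose residual correlation with intentions is 0.2 or more, the false-mediator rate is about 67–78% in the single model and about 43–50% per construct in the joint model (the latter computed at r = 0.3–0.5 with all seven moved). Outside those conditions the single-model rate is much lower: about 26–33% at r = 0.1, 22–26% at d = 0.15, about 5% with no ladder effect on the construct. Both r and the ladder effect on six of the seven constructs are assumptions.

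A reader might also infer that the 90-day survey can settle the question. It cannot, because a shared cause that persists passes the lagged model as often as real mediation does. The tests of H1 and RQ1 are not affected. The change is worth making before analysis because it costs little and H2 is the plan's account of how the ladder works.

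**What to change.** In the H2 row of Table 2 and in Main Analyses:

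- **Covariates.** Always adjust both the mediator and the intentions equations for a named set of pre-display characteristics: baseline minutes per week, age, sex, education, race/ethnicity and personal diagnoses. Do not select them by significance. The note to Table 1 reserves the screener's race and education items for recruitment stratification, so take these two from the Risk Assessment if it asks them, or amend the note.
- **Sensitivity value.** For each mediator, report the residual correlation with intentions at which the indirect effect is zero. Present it as a description of robustness, with no pass/fail threshold.
- **Wording.** State the no-unmeasured-confounding assumption. Report any significant indirect effect, from single or joint models, as *consistent with mediation* and not as demonstrated mediation.
- **90-day intentions.** A model with this outcome may be reported as supportive only, not as a criterion. First reconcile Table 1, which says the follow-up uses "the same items as in Baseline Survey 2 assessing intentions" and other constructs but lists no intentions items under Baseline Survey 2.

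The cost is a few lines of text, a little more analysis on data already planned, and a weaker secondary claim. No new visit or item is needed. Adjustment removes confounding only by what is measured, so the wording change is needed whatever the covariate set.

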Cronbach α will be used to test the internal consistency of multi-item constructs in Baseline Survey 1 (i.e., cognitive and affective perceived risk; response efficacy; action self-efficacy; affective reaction to the information; affective attitude about exercise; anticipated regret; intentions to engage in physical activity, message acceptance), Baseline Survey 2 (i.e., message acceptance, perceived clarity and vividness of images), and the Follow-Up Survey (i.e., intentions, action self-efficacy, cognitive and affective perceived risk, response efficacy, anticipated regret, affective attitude about exercise). Where $\alpha \geq .70$ we will create a scale by averaging responses to a given construct across diseases. That average score will be used in subsequent analyses. Comprehension, numeracy, and graph literacy will each be operationalized as continuous variables comprised of the number of items answered correctly.

Next, we will verify that participant characteristics (i.e., demographics, personal diagnosis of one of the target

diseases, self-reported health status, numeracy, health literacy, graph literacy, pre-intervention minutes of physical activity per week) are equivalent across experimental conditions by conducting t-tests, one-way ANOVAs, chi-square tests, or other tests, as appropriate. If any differences are found, these variables will be included in subsequent analyses as potential covariates. Personal characteristics will also be explored to determine if they are related to the outcomes of interest. Any characteristic that has a significant association with the outcomes will be included in subsequent analyses as potential covariates.

Main Analyses

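### Apart from sex, the covariates in the primary H1/RQ1 models are chosen by tests on the trial's own data, and nothing keeps out four candidates measured after the randomised display

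*Combined protocol and SAP*

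**What the plan says.** Statistical Considerations, Preliminary Analyses, lists the characteristics to be tested for equivalence across conditions: demographics, diagnosis of a target disease, self-reported health status, numeracy, health literacy, graph literacy and pre-intervention activity minutes. There are two ways into the models. For imbalance: "If any differences are found, these variables will be included in subsequent analyses as potential covariates". For association with an outcome: "Any characteristic that has a significant association with the outcomes will be included in subsequent analyses as potential covariates".

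Main Analyses fixes sex as a covariate and leaves the rest open: "The inclusion of other personal characteristics as covariates will be determined by the results of the preliminary analyses". Table 2 gives H1/RQ1 as a three-arm ANOVA with two planned contrasts and lists only risk presentation condition as predictor.

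Table 1 places numeracy, graph literacy, health literacy and self-reported health status in Baseline Survey 1, timed "Immediately following provision of personalized risk information". Procedure, Part 1, gives the same order. First "the participant will provide information about their demographics, health behaviors, and personal and family health history". Then "Results are displayed either as alphanumeric text, table, or risk ladder". Then "Afterwards, the participant will complete Baseline Survey 1 independently on paper".

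**The concern.** There are two separate problems.

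First, the primary models are not defined until the outcome data have been examined. The phrase about potential covariates does not make inclusion certain, but it adds discretion and removes none.

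Second, four named candidates are post-intervention variables for the display comparison. Adjusting for something that the randomised format may have changed can bias the randomised contrast in either direction. The imbalance rule works the wrong way here, because a score that the format has moved is more likely to be flagged. The Background gives a reason to expect selection for comprehension: "Demographics, numeracy, health literacy, and graph literacy were added because they are associated with the ability to understand and use health risk information". It gives no correlation with intentions, so weak correlations may apply to that outcome.

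The same timing affects RQ3, which uses numeracy, health literacy and graph literacy as moderators of a display that precedes their measurement. It does not affect H5, because Baseline Survey 1 is completed before the imagery task.

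**Working it through.** **The plan's own figure.** Sample Size Calculations, Risk Calculator: three groups, f = 0.15, alpha 0.05, 80% power. Noncentral F with lambda = N x f² = 432 x 0.0225 = 9.72 gives power 80.1%, and 432 is the smallest N that reaches 80%. With 10% missing, 432/0.90 = 480. Both figures reproduce, so the sample size is not in question. Equal allocation gives 432/3 = 144 per display arm.

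**Selection alone.** Both selection rules were applied mechanically to candidates that the display does not affect. With eight independent candidates (3,000 trials per scenario), F-test type I error was 4.2-4.9%. A second check with seven candidates and slopes 0-0.3 (4,000 runs each) gave 4.7-5.3% for ladder versus text. Neither simulates discretionary choice among flagged variables.

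**Bias from adjusting for an affected score.** Let outcome y = d x ladder + r x g + sqrt(1 - r²) x e, and let the measured score be m = g + s x ladder. Substituting g = m - s x ladder, the ladder coefficient after adjusting for m is d - r x s. The bias is therefore -r x s, and it is zero when s = 0. An effect common to all arms cancels; only a format-specific shift matters. The standard error is sqrt(1 - r²) x sqrt(2/144) = 0.118 x sqrt(1 - r²).

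Neither r nor s is in the documents; both are assumed. For d = 0, one affected covariate, always adjusted for:

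| r | shift (SD) | size of bias (SD) | false positives, normal approximation | simulated (10,000 runs) |
|---|---|---|---|---|
| 0.1 | 0.1 | 0.01 | 5.1% | 5.0% |
| 0.1 | 0.2 | 0.02 | 5.3% | 5.2-5.3% |
| 0.2 | 0.1 | 0.02 | 5.3% | 5.3-5.8% |
| 0.2 | 0.2 | 0.04 | 6.4% | 6.3-7.0% |
| 0.3 | 0.1 | 0.03 | 5.8% | 6.0-6.6% |
| 0.3 | 0.2 | 0.06 | 8.3% | 8.1-8.8% |
| 0.5 | 0.1 | 0.05 | 7.8% | 7.8-8.0% |
| 0.5 | 0.2 | 0.10 | 16.5% | 15.9-16.9% |

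Example for the last row: 0.10/(0.118 x 0.866) = 0.98 standard errors, so the two-sided rejection rate is about 16.5%.

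For a true effect of 0.30 SD at r 0.3-0.5, a +0.2 shift gives estimates of 0.24-0.20 SD (power 57-49%) and a -0.2 shift gives 0.36-0.40 SD.

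If all four scores shifted together, each with an assumed slope of 0.2, the bias at shifts of 0.1 and 0.2 SD would be about 4 x 0.2 x 0.1 = 0.08 and 4 x 0.2 x 0.2 = 0.16 SD, with F-test type I error of 12% and 37%.

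**How often the rules flag such a score.** Association rule: 43-64% of runs at r 0.1, 97-99% at r 0.2, about 100% from r 0.3. Imbalance rule: 5%, 12-13% and 39-41% at shifts of 0, 0.1 and 0.2 SD. Flagging is not certain inclusion.

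**Power reference.** Unadjusted contrast power at d = 0.30 is 71.9% (noncentral t, 429 df). With only the ladder arm shifted, f = 0.30 x sqrt(2)/3 = 0.141, below the plan's 0.15. At f = 0.15 the contrast is d = 0.15 x 3/sqrt(2) = 0.318 in that pattern (power 76.8%), or 0.15 x sqrt(6) = 0.367 with evenly spaced means (87.4%).

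**Mediation (H2, H4).** The mediator-to-outcome path is not randomised, so the four measures are plausible confounders there. With no true comprehension-to-intentions effect, and assumed numeracy correlations of 0.3-0.5 with comprehension and 0.1-0.3 with intentions (4,000 runs, joint-significance test, not the plan's bootstrap), leaving numeracy out gave false mediation in 6-53% of runs; including it gave 3-5%. But if numeracy is also put in the display-to-mediator equation, the same bias returns. At r 0.5, shift +0.2 and a true mediator-to-outcome path of 0.30, the display path falls from 0.30 to 0.20 and the indirect effect from 0.30 x 0.30 = 0.09 to 0.20 x 0.30 = 0.06.

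**The case against.** The best reply is that all the quantified harm is conditional. Every arm receives personalised results and only the format differs, numeracy and literacy may be fairly stable, and the documents report no format effect on any of these scores. At the low end of the assumed range the false-positive rate hardly leaves 5%. The four measures are also unlikely to be equally exposed: graph literacy tested just after viewing a ladder is a more natural candidate for a shift than numeracy. All of this stands, and it makes the timing issue a safeguard and not a demonstrated error.

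It can also be said that Table 2 lists no covariates for H1/RQ1 and that the non-parametric fallback makes adjustment uncertain. The bias figures do presume a parametric adjusted model. But neither point fixes the model, since Main Analyses still leaves the covariates to the preliminary results.

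A reader might infer three stronger things that the documents do not support. One is that choosing covariates by significance inflates type I error here; mechanical use with unaffected candidates did not. Another is that the ladder contrast will be biased; that needs a format-specific shift for which there is no evidence. The third is that 72% contrast power shows a shortfall against the plan's 80%; the two figures refer to different tests and different effect sizes.

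**Conclusion.** The point holds in two parts of different strength. It is certain from the text that the H1/RQ1 models are not fixed before outcomes are seen, and that four post-display measures are eligible for them. The consequence of the timing is conditional: bias of about -r x shift, which is 0.01-0.04 SD with 5-7% false positives at r 0.1-0.2 and shift 0.1-0.2 SD, and 0.06-0.10 SD with 8-17% at r 0.3-0.5 and shift 0.2 SD. Those figures assume one affected covariate, 144 per arm, and adjustment always made. The plan neither states nor checks the no-shift assumption on which an unbiased adjusted contrast would rest. The change should be made, with medium confidence as to its practical importance.

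**What to change.** In Preliminary Analyses and Main Analyses, replace both significance-based rules with a list of covariates named in advance, and describe characteristics by arm without tests.

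- **H1/RQ1, H3, RQ2:** limit the main model to variables recorded before the display, for example sex, age, personal diagnosis of a target disease, baseline minutes per week, race/ethnicity and education. Take the last two from the website risk assessment if they are collected there, because the note to Table 1 reserves the screener versions for recruitment stratification. A model that adds the four Baseline Survey 1 measures can be a named sensitivity analysis.
- **H2, H4:** name the four measures in advance as confounders in the mediator-to-outcome equation only, and leave them out of the display-to-mediator equation.
- **H5:** they may be kept if named in advance.
- **RQ3:** report numeracy, health literacy and graph literacy by display arm, and state that moderation by them assumes no display effect on the scores.

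The cost is SAP wording; questionnaires, website and sample size are unchanged. If the format does not affect the scores, the main H1/RQ1 model gives up some precision: contrast power of about 72% instead of 75-84% at assumed r 0.3-0.5 and d 0.30, and almost nothing at r 0.1-0.2. Part of this is recoverable: pre-display covariates explaining an assumed 2%, 5% or 10% of outcome variance give 72.8%, 74.1% or 76.3%.
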